Appendix 3 Eastern Cooperative Oncology Group Performance Status

Scale	ECOG Status
0	Fully active, able to carry on all predisease performance without restriction.
1	Restricted in physically strenuous activity but ambulatory and able to carry out work of a light or sedentary nature (eg, light house work, office work).
2	Ambulatory and capable of all self-care, but unable to carry out any work activities. Up and about more than 50% of waking hours.
3	Capable of only limited self-care, confined to bed or chair more than 50% of waking hours.
4	Completely disabled. Cannot carry on any self-care. Totally confined to bed or chair.
5	Dead.

ECOG = Eastern Cooperative Oncology Group.

Adapted from Oken MM, et al. Am J Clin Oncol. 1982;5:649-55.

Appendix 4 Cockcroft and Gault Formula

$$\text{Male} \quad \frac{(140-\text{age}) \times \text{weight (kg)}}{\text{Serum creatinine (mg/dL)} \times 72} = \text{XX mL/min}$$

$$\text{Female} \quad \frac{(140-\text{age}) \times \text{weight (kg)} \times 0.85}{\text{Serum creatinine (mg/dL)} \times 72} = \text{XX mL/min}$$

Adapted from Cockcroft DW, et al. Nephron. 1976;16(1):31-41.

For serum creatinine measured in $\mu\text{mol/L}$:

$$\text{Male} \quad \frac{(140-\text{age}) \times \text{weight (kg)} \times 1.23}{\text{Creatinine } (\mu\text{mol/L})} = \text{XX mL/min}$$

$$\text{Female} \quad \frac{(140-\text{age}) \times \text{weight (kg)} \times 1.23 \times 0.85}{\text{Creatinine } (\mu\text{mol/L})} = \text{XX mL/min}$$

Appendix 5 New York Heart Association Cardiac Disease Classification

The New York Heart Association Cardiac Disease Classification provides a functional and therapeutic classification for the prescription of physical activity for cardiac subjects. Based on NYHA definitions, subjects are to be classified as follows:

Class	NYHA Status
Class I:	Subjects with no limitation of activities; they suffer no symptoms from ordinary activities.
Class II:	Subjects with slight, mild limitation of activity; they are comfortable with rest or with mild exertion.
Class III:	Subjects with marked limitation of activity; they are comfortable only at rest.
Class IV:	Subjects who should be at complete rest, confined to bed or chair; any physical activity brings on discomfort and symptoms occur at rest.

NYHA = New York Heart Association.

Adapted from The Criteria Committee of the New York Heart Association. Nomenclature and Criteria for Diagnosis of Diseases of the Heart and Great Vessels. 9th ed. 1994:253-6.

Appendix 6 Common Terminology Criteria for Adverse Events (v4.03)

The National Cancer Institute's CTCAE v4.0 published 28 May 2009 (v4.03: June 14, 2010) provides descriptive terminology to be used for AE reporting in clinical trials. A brief definition is provided to clarify the meaning of each AE term. To increase the accuracy of AE reporting, all AE terms in CTCAE version 4.0 have been correlated with single-concept, MedDRA terms.

Grades in CTCAEs v4.03 refer to the severity of the AE. Grades of 1 through 5, with unique clinical descriptions of severity for each AE, are based on this general guideline:

Grade	CTCAE Status
1	Mild: asymptomatic or mild symptoms; clinical or diagnostic observations only; intervention not indicated.
2	Moderate: minimal, local, or noninvasive intervention indicated; limiting age-appropriate instrumental activities of daily living (ADL). ^a
3	Severe or medically significant but not immediately life-threatening: hospitalization or prolongation of hospitalization indicated; disabling, limiting self-care ADL. ^b
4	Life-threatening consequences: urgent intervention indicated.
5	Death related to adverse event.

CTCAE = Common Terminology Criteria for Adverse Events.

a: Instrumental ADL refers to preparing meals, shopping for groceries or clothes, using the telephone, managing money, etc.

b: Self-care ADL refers to bathing, dressing and undressing, feeding self, using the toilet, taking medications, and not bedridden.

Adapted from the Cancer Therapy Evaluation Program, NCI. CTCAE v4.0. Available from:

<http://evs.nci.nih.gov/ftp1/CTCAE/About.html> (Accessed 02 Oct 2014).

For further details regarding MedDRA, refer to the MedDRA website at: <http://www.meddrasso.com>. CTCAE v4.0 is available online at: <http://evs.nci.nih.gov/ftp1/CTCAE/About.html> (Accessed 02 Oct 2014).

Appendix 7 Sponsor's Grading for Laboratory Values

	Grade 1	Grade 2	Grade 3	Grade 4
BLOOD/BONE MARROW				
Hemoglobin	<LLN – 10.0 g/dL <LLN – 100 g/L <LLN – 6.2 mmol/L	<10.0 – 8.0 g/dL <100 – 80 g/L <6.2 – 4.9 mmol/L	<8.0 g/dL <80 g/L <4.9 mmol/L; transfusion indicated	life-threatening consequences; urgent intervention indicated
Leukocytes (total WBCs)	<LLN – 3.0×10 ⁹ /L <LLN – 3000/mm ³	<3.0 – 2.0×10 ⁹ /L <3000 – 2000/mm ³	<2.0 – 1.0×10 ⁹ /L <2000 – 1000/mm ³	<1.0×10 ⁹ /L <1000/mm ³
Lymphocytes	<LLN – 800/mm ³ <LLN – 0.8×10 ⁹ /L	<800 – 500/mm ³ <0.8 – 0.5×10 ⁹ /L	<500 – 200/mm ³ <0.5 – 0.2×10 ⁹ /L	<200/mm ³ <0.2×10 ⁹ /L
Neutrophils	<LLN – 1.5×10 ⁹ /L <LLN – 1500/mm ³	<1.5 – 1.0×10 ⁹ /L <1500 – 1000/mm ³	<1.0 – 0.5×10 ⁹ /L <1000 – 500/mm ³	<0.5×10 ⁹ /L <500/mm ³
Platelets	<LLN – 75.0×10 ⁹ /L <LLN – 75,000/mm ³	<75.0 – 50.0×10 ⁹ /L <75,000 – 50,000/mm ³	<50.0 – 25.0×10 ⁹ /L <50,000 – 25,000/mm ³	<25.0×10 ⁹ /L <25,000/mm ³
METABOLIC/ LABORATORY				
Albumin, serum- low (hypoalbuminemia)	<LLN – 3 g/dL <LLN – 30 g/L	<3 – 2 g/dL <30 – 20 g/L	<2 g/dL <20 g/L	life-threatening consequences; urgent intervention indicated
Alkaline phosphatase	>ULN – 3.0×ULN	>3.0 – 5.0×ULN	>5.0 – 20.0×ULN	>20.0×ULN
ALT	>ULN – 3.0×ULN	>3.0 – 5.0×ULN	>5.0 – 20.0×ULN	>20.0×ULN
AST	>ULN – 3.0×ULN	>3.0 – 5.0×ULN	>5.0 – 20.0×ULN	>20.0×ULN
Bilirubin (hyperbilirubinemia)	>ULN – 1.5×ULN	>1.5 – 3.0×ULN	>3.0 – 10.0×ULN	>10.0×ULN
Calcium, serum-low (hypocalcemia)	<LLN – 8.0 mg/dL <LLN – 2.0 mmol/L	<8.0 – 7.0 mg/dL <2.0 – 1.75 mmol/L	<7.0 – 6.0 mg/dL <1.75 – 1.5 mmol/L	<6.0 mg/dL <1.5 mmol/L
Calcium, serum-high (hypercalcemia)	>ULN – 11.5 mg/dL >ULN – 2.9 mmol/L	>11.5 – 12.5 mg/dL >2.9 – 3.1 mmol/L	>12.5 – 13.5 mg/dL >3.1 – 3.4 mmol/L	>13.5 mg/dL >3.4 mmol/L
Cholesterol, serum-high (hypercholesterolemia)	>ULN – 300 mg/dL >ULN – 7.75 mmol/L	>300 – 400 mg/dL >7.75 – 10.34 mmol/L	>400 – 500 mg/dL >10.34 – 12.92 mmol/L	>500 mg/dL >12.92 mmol/L
Creatinine	>ULN – 1.5×ULN	>1.5 – 3.0×ULN	>3.0 – 6.0×ULN	>6.0×ULN

Sponsor's Grading for Laboratory Values

	Grade 1	Grade 2	Grade 3	Grade 4
GGT (γ -glutamyl transpeptidase)	>ULN – 3.0×ULN	>3.0 – 5.0×ULN	>5.0 – 20.0×ULN	>20.0×ULN
Glucose, serum-high (hyperglycemia)	Fasting glucose value: >ULN – 160 mg/dL >ULN – 8.9 mmol/L	Fasting glucose value: >160 – 250 mg/dL >8.9 – 13.9 mmol/L	>250 – 500 mg/dL; >13.9 – 27.8 mmol/L; hospitalization indicated	>500 mg/dL; >27.8 mmol/L; life-threatening consequences

## 2 LIST OF ABBREVIATIONS AND DEFINITIONS OF TERMS

Abbreviation	Term
AE	adverse event
ALP	alkaline phosphatase
ALT	alanine aminotransferase
ANC	absolute neutrophil count
AST	aspartate aminotransferase
ATC	anaplastic thyroid cancer
β-hCG	beta-human chorionic gonadotropin
BOR	best overall response
BP	blood pressure
CBR	clinical benefit rate
CI	confidence interval
CR	complete response
CRF	case report form
CSR	clinical study report
CT	computerized tomography
CTCAE	Common Terminology Criteria for Adverse Events
DCR	disease control rate
DOR	duration of response
EAS	evaluable analysis set
ECG	electrocardiogram
ECOG	Eastern Cooperative Oncology Group
FAS	full analysis set
FDA	Food and Drug Administration
ICF	Informed consent form
INR	International Normalized Ratio
KM	Kaplan-Meier
MedDRA ®	Medical Dictionary for Regulatory Activities
MRI	magnetic resonance imaging
NCI	National Cancer Institute
NYHA	New York Heart Association

Abbreviation	Term
ORR	objective response rate
OS	overall survival
PE	physical examinations
PET	positron emission tomography
PFS	progression-free survival
PI	principal investigator
PR	partial response
PRES	posterior reversible encephalopathy syndrome
PT	preferred term
QD	once a day
RBC	red blood cell count
RECIST	Response Evaluation Criteria in Solid Tumors
RR-DTC	radioiodine-refractory differentiated thyroid cancer
RTK	receptor tyrosine kinase
SAE	serious adverse events
SAP	statistical analysis plan
SD	stable disease
SmPC	Summary of Product Characteristics
SOC	system organ class
SUSAR	suspected unexpected serious adverse reactions
T4	thyroxine
TEAE	treatment-emergent adverse event
TSH	thyroid stimulating hormone
TTP	time to progression
ULN	upper limit of normal
US	United States
VEGF	vascular endothelial growth factor

### 3 INTRODUCTION

The purpose of this statistical analysis plan (SAP) is to describe the procedures and the statistical methods that will be used to analyze and report results for Eisai Protocol E7080-M000-213, an Open-Label, Single-Arm, Multicenter, Phase 2 Trial of Lenvatinib for the Treatment of Anaplastic Thyroid Cancer (ATC). The focus of this SAP is on all the analyses specified in the final protocol of the study (i.e., Version 3.0 dated on 24May2016, Amendment 02), which covers the both interim analyses and final analyses. This SAP will be finalized before the database lock of study completion.

#### 3.1 Study Objectives

##### 3.1.1 Primary Objective

To evaluate objective response rate ([ORR]: complete response [CR] or partial response [PR]) by investigator review in subjects with anaplastic thyroid cancer (ATC) treated with lenvatinib.

##### 3.1.2 Secondary Objectives

- To evaluate 12-week progression-free survival (PFS)
- To evaluate 6-month overall survival (OS)
- To evaluate median PFS and median OS
- To evaluate safety and tolerability of lenvatinib in subjects with ATC

##### 3.1.3 Exploratory Objectives

- To explore clinical benefit rate ([CBR]: CR, PR or durable stable disease [SD]  $\geq 23$  weeks)
- To explore disease control rate ([DCR]: CR, PR or SD)
- To explore duration of response (DOR)
- To identify and explore tumor and blood biomarkers that correlate with clinical outcomes, including efficacy

#### 3.2 Overall Study Design and Plan

This was an open-label, single arm, multicenter, Phase 2 trial of lenvatinib (24 mg/day) to assess the efficacy and safety of lenvatinib in subjects with ATC. The study was designed primarily to provide additional efficacy and safety data for single-agent lenvatinib in a larger cohort of ATC subjects. Approximately a total of 76 subjects was planned to be enrolled into this study (i.e., signed informed consent) to be sure that out of the 76 subjects there would be 57 subjects confirmed with ATC for the purpose of efficacy analyses. Also one interim analysis was planned to be performed after the first 20 evaluable subjects completed at least 2 tumor assessments or discontinue treatment due to any reason. While waiting for the

interim analysis results the enrollment would not be suspended so that no enrollment gap was in the study for the interim analysis. From the interim analysis the enrollment would be halted if the number of responders was 3 or less (ORR  $\leq$ 15%, according to Response Evaluation Criteria in Solid Tumors (RECIST) 1.1), and the safety and efficacy data would be further evaluated before making the decision of stopping the study permanently.

This study would consist of the following three phases and the corresponding procedures/assessments to each was presented as Table 4 in the final protocol of the study in details, where as shown a 28-days during the treatment period was considered as one cycle of treatment and used for study related visits/assessments:

- The **Pretreatment Phase:** including Screening period from Day -21 prior to the first study treatment of lenvatinib start. All analyses related baseline assessments would be defined as the last assessment obtained during this phase for each.
- The **Treatment Phase:** starting from the time of the first lenvatinib administration till the end of last lenvatinib administration. Subjects would be treated with lenvatinib dose of 24 mg once daily by oral administration, or dose following protocol on treatment adjustment.
- The **Posttreatment Phase:** starting after the last study dose, including End of Treatment visit (i.e., within 30 days of last dose), survival follow-ups (i.e., every 12 ( $\pm$ 1) weeks after End of Treatment visit).

## 4 DETERMINATION OF SAMPLE SIZE

The sample size calculation was based on the assumed objective response rate (ORR), defined in Section 5.1) of 27% in the trial as compared to 10% in the historical control. Using a binomial exact test, the power was 0.932 with 57 evaluable subjects to demonstrate statistical significance at a 1-sided alpha of 0.025. To evaluate the power in the secondary endpoint 12-week PFS (defined in Section 5.1), an exponential distribution assuming 12-week PFS being 70% was used to simulate PFS data. Censoring times were generated such that the average number of observed PFS events was approximately 45 in the 57 evaluable subjects. In the 5,000 simulation runs, the lower bound of 95% confidence interval for PFS at 12 weeks was greater than 50% (historical control), 87.7% of the time. Hence, the power was 0.877 in demonstrating statistical superiority of the 12-week PFS in single agent lenvatinib. Similarly, approximately 35 observed OS events in 57 evaluable subjects yielded a power of approximately 0.857 in demonstrating a statistically significant increase in 6-month OS over historical control. Assuming ATC confirmation rate was 75% in the enrolled subjects, approximately 76 subjects would need to be enrolled. Subjects deemed to have another diagnosis (not ATC) would be replaced for the purpose of efficacy analyses.

## 5 STATISTICAL METHODS

All descriptive statistics for continuous variables will be reported in mean, standard deviation (SD), median, 25 percentile (Q1), 75 percentile (Q3), minimum and maximum. Categorical variables will be summarized in number (percentage) of subjects.

### 5.1 Study Endpoints

All tumor related endpoints, including timepoint tumor responses and the best overall responses (i.e., complete response, partial response, stable disease, disease progression), are from investigators based on RECIST 1.1.

#### 5.1.1 Primary Endpoint

The primary efficacy endpoint is ORR as determined by investigator review, using RECIST 1.1. ORR is the proportion of subjects who have best overall response (BOR) of CR or PR (confirmed). Confirmation of CR or PR must be performed at least 28 days following the initial achievement of the response.

#### 5.1.2 Secondary Endpoints

- **Twelve-week PFS** is the percentage of subjects in the analysis population who remain alive and disease progression-free at 12 weeks post first study dose. This will be the Kaplan-Meier estimated rate of event (death or disease progression)-free at 12 weeks post first study dose (i.e., at the 84th day counting from the first dose date),
- **Six-month OS** is defined as the percentage of subjects in the analysis population who are alive at 6 months post first study dose. This will be the Kaplan-Meier estimated

rate of event (death)-free at 6 months post first study dose (i.e., at the 183th day counting from the first dose date, from  $6 \times 365.25/12$ ),

- **Median PFS and Median OS.** These will be the estimated median event-free time from Kaplan-Meier method (in day and month). The PFS is defined as the time from the date of first dose of study drug to date of first documentation of disease progression (only from the radiological assessment) or death, whichever occurs first, and OS is defined as the time from the date of first dose of study drug until date of death from any cause.

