9.1.2 Treatment Phase

The Treatment Phase will begin at the time of lenvatinib administration on C1D1 and end following the last dose of lenvatinib. Subjects will be treated with lenvatinib dose of 24 mg (2 capsules of 10 mg each and 1 capsule of 4 mg) once daily by oral administration. Subjects will undergo safety and efficacy assessments. Subjects will discontinue treatment with lenvatinib at the time of disease progression (radiological or clinical), development of unacceptable toxicity (AE), lost to follow-up, withdrawal of consent, subject choice, pregnancy, or study termination by the sponsor.

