9.3.3 Removal of Subjects From Therapy or Assessment

The investigator may discontinue treating a subject with study treatment or withdraw the subject from the study at any time for safety or administrative reasons. The subject may decide to discontinue study treatment or withdraw from the study at any time for any reason. The reason for discontinuation will be documented. If a subject discontinues study treatment, the subject will enter the Follow-Up Period and complete protocol-specified off-treatment visits, procedures, and survival follow-up unless the subject withdraws consent. The investigator should confirm whether a subject will withdraw from study treatment but agree to continue protocol-specified, off-treatment study visits, procedures, and survival follow-up, or whether the subject will withdraw consent. If a subject withdraws consent, the date will be documented in the source documents. The Subject Disposition CRF page will be completed indicating the primary reason for discontinuation and all other reason(s)

contributing to the subject's discontinuation from treatment. In addition, the date of last dose of study drug will be recorded on the Study Drug Dosing CRF page.

During the Follow-Up Period, in subjects who have discontinued study treatment without documented disease progression (radiological or clinical), every effort should be made to continue monitoring their disease status by radiologic imaging every 6 weeks \pm 1 week for the first 24 weeks and every 8 weeks \pm 1 week thereafter from the date of the last assessment until (1) the start of new anticancer treatment, (2) disease progression (3) death, or (4) the end of the study, whichever occurs first.

All subjects will be followed for survival until death, except where a subject withdraws consent or the sponsor chooses to halt survival follow-up after completion of the primary study analysis.

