9.7.2 Determination of Sample Size

The sample size calculation was based on the assumed ORR of 27% in the trial as compared to 10% in the historical control. Using a binomial exact test, the power is 0.932 with 57 evaluable subjects to demonstrate statistical significance at a 1-sided alpha of 0.025. To evaluate the power in the secondary endpoint 12-week PFS, an exponential distribution assuming 12-week PFS being 70% was used to simulate PFS data. Censoring times were generated such that the average number of observed PFS events was approximately 45 in the 57 evaluable subjects. In the 5,000 simulation runs, the lower bound of 95% CI for PFS at 12 weeks was greater than 50% (historical control), 87.7% of the time. Hence, the power is 0.877 in demonstrating statistical superiority of the 12-week PFS in single agent lenvatinib. Similarly, approximately 35 observed OS events in 57 evaluable subjects yield a power of approximately 0.857 in demonstrating a statistically significant increase in 6-month OS over historical control. Assuming ATC confirmation rate is 75% in the enrolled subjects, approximately 76 subjects will need to be enrolled. Subjects deemed to have another diagnosis (not ATC) will be replaced for the purpose of efficacy analyses.

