Progressive Disease (PD)	At least a 20% increase in the sum of the LD of target lesions, taking as reference the smallest sum LD recorded at Baseline or during treatment. The sum must also have an absolute increase of ≥ 5 mm.
Stable Disease (SD)	Neither sufficient shrinkage to qualify for PR nor sufficient increase to qualify for PD, taking as reference the smallest sum LD since the treatment started
Not Evaluable (NE)	No imaging/measurement done at all or only on a subset of lesions at a particular time point; a target lesion at Baseline that is subsequently not measured or that is unable to be evaluated. Includes scans that are not performed at a specified time point to evaluate the target lesion(s).

Table 2 Evaluation of Nontarget Lesions

Complete Response (CR)	Disappearance of all nontarget lesions. All lymph nodes <10 mm (short axis)
Non-CR/Non-PD	Persistence of 1 or more nontarget lesion(s)
Progressive Disease (PD)	Unequivocal progression (substantial worsening in nontarget disease such that overall tumor burden has increased sufficiently to warrant discontinuation of therapy); unequivocal progression of existing nontarget lesions ^a
Not Evaluable (NE)	A nontarget lesion at Baseline that is subsequently not measured or that is unable to be evaluated

a: Although a clear progression of "nontarget" lesions only is exceptional, in such circumstances, the opinion of the site radiologist should prevail.

Table 3 Overall Response at Each Assessment Time Point for Subjects with Target (\pm Nontarget) Disease

Target Lesions	Nontarget Lesions	New Lesions	Overall Response
CR	CR	No	CR
CR	Non-CR/Non-PD	No	PR
CR	Not evaluated	No	PR
PR	Non-PD or not all evaluated	No	PR
SD	Non-PD or not all evaluated	No	SD
Not all evaluated	Non-PD	No	NE
PD	Any	Yes or No	PD
Any	PD	Yes or No	PD
Any	Any	Yes	PD

CR = complete response, NE = not evaluable, PD = disease progression, PR = partial response, SD = stable disease.

Subjects with a global deterioration of health status requiring discontinuation of treatment without objective evidence of PD at that time point assessment should be classified as having "symptomatic deterioration." Every effort should be made to document objective progression after discontinuation of treatment.

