**Table 2 Censoring Rules for Analysis of Progression-Free Survival**

No.	Situation	Date of Progression or Censoring	Outcome
1	No baseline tumor assessments	Date of first dose	Censored
2	Progression documented between scheduled visits	Date of first radiological PD assessment	Progressed
3	No progression at the time of data cut-off or withdrawal from study	Date of last adequate radiologic assessment prior to or on date of data cut-off or withdrawal from study, or date of the first dose if no adequate post baseline tumor assessment was conducted.	Censored
4	New anticancer treatment started	Date of last adequate radiologic assessment prior to or on date of new anticancer treatment, or date of the first dose if no adequate post baseline tumor assessment was conducted.	Censored
5	Death before first PD assessment	Date of death	Progressed
6	Death between adequate assessment visits*	Date of death	Progressed
7	Death or progression after two or more missed visits**	Date of last adequate radiologic assessment before missed tumor assessments, or date of the first dose if no adequate post baseline tumor assessment was conducted.	Censored
8	No post-baseline tumor assessments but known alive	Date of first dose	Censored

CR = complete response, PD = progressive disease, PR = partial response, SD = stable disease,

\* Adequate tumor assessment is a radiologic assessment of CR, PR, SD, non-CR/non-PD or PD as determined by investigators.

New anticancer treatment includes palliative radiotherapy. Any tumor assessments after new anticancer treatment started will be removed in the definition of PFS.

\*\* 'More than two missed visits' occurs if the duration between the last tumor assessment and death or PD is longer than the following:

[figure not shown]
1. 12 weeks if the last tumor assessment is prior to week 24
2. 16 weeks if the last tumor assessment is on or after week 24

Note: NE counts as a non-missing visit for No. 7.

Censoring rules are also described in [Figure 1](#).

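### PFS counts only radiological progression or death, and the plan has no rule or sensitivity analysis for clinical progression without confirming imaging, so 12-week PFS leans upward against the fixed 50%

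*SAP*

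**What the plan says.** **Event.** SAP 5.1.2 measures PFS from first dose to death or to first documented progression, the latter taken "only from the radiological assessment".

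**Treatment.** Protocol 9.1.2 has subjects stop lenvatinib "at the time of disease progression (radiological or clinical"), among other reasons. SAP 3.2 agrees.

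**Imaging after treatment.** Protocol 9.3.3 asks for continued radiologic monitoring in subjects who stopped "without documented disease progression (radiological or clinical"), and SAP 3.2 repeats the restriction. Protocol 9.1.3, Protocol 9.5.1.3.1 and Table 4 footnotes c and u continue scans until progression or new anticancer therapy, without mentioning clinical progression.

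**Provisions that help.**
- Protocol 9.7.1.6.2 asks for an MRI, where possible, when progression is judged clinically. If the MRI confirms it, its date is the progression date.
- Table 4 footnote u asks for a CT/MRI near Week 6 in subjects who leave before that scan, ahead of any new therapy.
- Appendix 2 says of subjects who stop for global deterioration without objective progression: "Every effort should be made to document objective progression after discontinuation of treatment".

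**Censoring.** SAP Table 2 has no row for clinical progression. Rows 3, 4 and 8 censor at the last adequate scan, or at first dose if there is none. Rows 5 and 6 count death at its date. Row 7 ("Death or progression after two or more missed visits") censors when the gap from the last scan exceeds 12 weeks, or 16 weeks if that scan was at week 24 or later.

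**Sensitivity analysis.** SAP 5.4.2 contains none for PFS, SAP 5.3.5 mentions sensitivity analysis without defining one, and SAP 5.7 plans no other analysis.

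**The concern.** Counting only radiological progression is a common choice and causes little trouble while scans continue. Here, under Protocol 9.3.3 and SAP 3.2, the judgement that stops treatment can also take the subject off the imaging schedule. Subjects who are deteriorating may then leave the risk set with no event, or with an event dated later than the deterioration. Kaplan-Meier assumes that censored subjects have the same prognosis as those still followed, which is unlikely for this group.

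At stake is the protocol's claim of superiority if the lower 95% limit for 12-week PFS exceeds 50%. With one arm and a fixed comparator, no control group shares the bias.

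**Working it through.** **1. What happens to a subject stopped for clinical progression with no RECIST progression yet**

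| Path | Treatment in PFS |
|---|---|
| Imaging confirms progression | Event at the scan date |
| No confirming scan, no new therapy, death inside the row 7 window | Event at death, later than the clinical date |
| No confirming scan, new anticancer therapy | Censored at last adequate scan or first dose (row 4) |
| No confirming scan, alive at cut-off or withdrawn | Censored at last adequate scan or first dose (rows 3, 8) |

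Only the first path dates the failure close to when it happened.

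**2. Reproducing the plan's power**

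Inputs from Protocol 9.7.2: "an exponential distribution assuming 12-week PFS being 70% was used to simulate PFS data"; the "average number of observed PFS events was approximately 45 in the 57 evaluable subjects"; and "the lower bound of 95% CI for PFS at 12 weeks was greater than 50% (historical control), 87.7% of the time".

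- Hazard: −ln(0.70)/12 = 0.0297 per week.
- Estimate: S(t) = Π(1 − dᵢ/nᵢ).
- Greenwood variance: S(t)² Σ dᵢ/[nᵢ(nᵢ − dᵢ)].
- Success: S(12) − 1.96·SE > 0.50.

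In 5,000 simulated trials of 57 subjects with about 45 events, power was 0.877 with exponential censoring, 0.874 with uniform censoring and 0.893 with administrative censoring only. The stated 0.877 is reproduced with the plain Greenwood interval.

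**3. Reference case: clinical progression counted as an event at its own date**

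With 4,000 runs, a true 12-week PFS of 50% (hazard ln 2/12 = 0.0578 per week) gave a mean estimate of 0.498 and false success of 3.0%. A true 70% gave 0.700 and power 0.896.

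**4. Plan as written**

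The documents give no share of progressions that are clinical only, so that share, f, is assumed to be 10-40%. Also assumed: 0 or 50% of these are confirmed by imaging, 0 or 30% start new therapy, and median survival after progression is 4 or 8 weeks. Deaths inside the 12/16-week window count as events. Radiological events keep their true times, to isolate this effect. At a true 50%:

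| f | Mean 12-week estimate | False success |
|---|---|---|
| 10% | 0.507-0.522 | 4-6% |
| 20% | 0.516-0.548 | 5-12% |
| 30% | 0.520-0.574 | 6-22% |
| 40% | 0.531-0.602 | 8-33% |

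At a true 70% the mean estimate was 0.705-0.773. Monte Carlo error is at most about 0.8 percentage points. The runs use the design's 57 subjects. SAP 5.4.2 places the secondary analyses in the FAS, where a different n would change the false-success rates.

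**5. Ceiling**

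If every clinical-only progressor were censored and later deaths ignored, censoring at the clinical date would give 0.5^(1−f): 0.536, 0.574, 0.616 and 0.660 for f = 10, 20, 30 and 40%. Simulation with censoring moved back to the last scan gave 0.531, 0.564, 0.602 and 0.641, with false success of 7, 17, 32 and 52%. The plan as written lies below this ceiling because some clinical progressors are confirmed by imaging or die within the window.

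**The case against.** **The safeguards are substantial.** A reader might infer that all clinical progressors are censored as event-free. The documents do not support that. A confirming MRI makes an event, deaths inside the window are events, and Protocol 7.1.1 gives a median survival of 3 to 5 months, so early deaths will be common. SAP section 7 does not withdraw the MRI provision. This stands, and it is why step 4 rather than the ceiling gives the relevant range. The safeguards remain partial. The MRI is asked for only where possible, with no rule if it is not done or does not confirm. Protocol 9.5.1.3.1 requires CT for the chest, while Protocol 7.1.1 lists lung as the commonest metastatic site (80%), so an MRI may not cover the progressing site. The Week 6 scan covers only those who leave before it.

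**Scanning may not stop.** It is tempting to say that clinical progression ends scheduled imaging. Protocol 9.3.3 and SAP 3.2 read that way, but Protocol 9.1.3, 9.5.1.3.1 and Table 4 do not. The wording is inconsistent and does not amount to a clear stop. Nor does Appendix 2 simply contradict 9.3.3: it also works as a safeguard, and 9.3.3 forbids no scan.

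**Row 7 may look like an aggravating factor.** For 12-week PFS it is not. A death more than 12 weeks after any post-dose scan falls after week 12. Counting it at its date would keep the subject event-free through week 12, so censoring earlier does not raise the 12-week estimate relative to counting that death.

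**The comparator is unknown.** The documents do not say whether the historical 50% counted clinical progression. If it did not, part of the bias would cancel. That remains open.

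**Clinical progression is subjective** in an open-label trial, in both occurrence and date. This is a good reason to keep the radiological definition as primary and not to make a sensitivity result a condition of the claim.

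**Conclusion.** The point holds in direction, with its size conditional on assumptions. The radiological definition is not the fault. The gap is the absence of a stated rule and a sensitivity analysis for clinical progression without confirming imaging, together with imaging instructions that differ between sections. Every simulated scenario with clinical-only progression overstated 12-week PFS.

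At a true 50% the overstatement runs from about 1 to 10 percentage points, and false success from about 4% to 33% against about 3%. The upper end needs 40% clinical-only progression, no confirmatory imaging, 30% new therapy and 8-week median post-progression survival together. At 10% clinical-only progression the effect is small (4-6% false success). None of these inputs is in the documents, so the range shows sensitivity and does not predict the actual bias.

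The primary ORR analysis and OS are unaffected. This is a cheap improvement to a secondary endpoint that carries a superiority claim.

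**What to change.** - Keep the radiological definition as the main analysis, and state in SAP Table 2 how clinical progression without confirming imaging is handled.
- Add to SAP 5.4.2 a pre-specified supportive analysis of 12-week PFS. Count discontinuation for disease progression without RECIST progression as an event at the clinical progression date, or at the last-dose date if no such date is recorded.
- Report how many subjects this affects, and read the 12-week PFS claim alongside the result, without making it a formal gate.
- Reconcile the off-treatment imaging wording in Protocol 9.3.3 and SAP 3.2 with Protocol 9.1.3, 9.5.1.3.1, 9.7.1.6.2, Table 4 footnotes c and u, and Appendix 2.

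The cost is SAP wording and one extra run. Protocol 9.5.5 lists disease progression as a discontinuation reason without separating clinical from radiological, and 9.3.3 records the last-dose date. Affected subjects can therefore be found by crossing that reason with the absence of RECIST progression. The documents do not show that a clinical progression date is collected, hence the last-dose proxy. The downside is a less favourable supporting estimate that rests on a more subjective event date.
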